10.2 Subject Samples

The main subject samples of interest are defined as follows.

The all subjects consented sample will consist of all subjects who:

- Gave their informed consent.

The all subjects <allocated to treatment> sample will consist of all subjects who:

- Were in the all subjects consented sample; and
- Were <allocated to treatment>.

The safety sample will consist of all subjects who:

- Were in the all subjects allocated to treatment sample; and
- Had at least one dose of study medication administered.

The full analysis (FA) sample will consist of all subjects who:

- Were included in the safety sample; and
- Had data for at least one post-baseline assessment of any efficacy measurement.

The per-protocol (PP) sample will be defined through blind data review and will consist of all subjects who:

- Were included in the FA sample; and
- Did not present any major protocol violation.

10.3 Efficacy

The primary efficacy variable is the duration (hours) of diarrhea (treatment duration max 5 days). Duration of diarrhea is defined by date of the evacuation of the last diarrheal/watery stool.

In order to compare the primary efficacy parameter, duration of diarrhea, between the treatment groups, a Kaplan Meier analysis will be performed. The log-rank test will be used to test whether the difference between the duration of diarrhea between two treatment groups is statistically significant, i.e. p-value <0.05.

The secondary efficacy variables are

- Number of stools at baseline and per treatment day for toilet-trained subjects, only
- Number of watery stools per day for toilet-trained subjects, only.
- Assessment of treatment success by the physician
- Time until recovery, defined by date and time of the evacuation of the first of two consecutive normal stools.
- Number of subjects recovered per treatment group, in total and until each individual treatment day
- Mean and median time until recovery per treatment group

The assessment of treatment success by the physician will be done using the Global Physician Assessment GPA score:

- 1 = Complete relief of acute diarrhea,
- 2 = marked improvement of acute diarrhea,
- 3 = moderate improvement of acute diarrhea,
- 4 = slight improvement of acute diarrhea,
- 5 = no change in acute diarrhea,
- 6 = worsening of acute diarrhea.

Treatment will be rated as success when the GPA score equals 1 or 2.

Secondary efficacy parameters will be analyzed similarly to the primary analysis. All parameters will also be summarized using descriptive statistics.

10.4 Safety

The safety sample will be used for the analysis of the safety and tolerability data.

AEs are considered treatment emergent (TE) if they start or worsen at or after the first administration of study drug and before or on the day of last administration of study drug plus a gap period of 1 day.

AEs will be reported on a per-subject basis, i.e. counting subjects rather than events. This means that if a subject suffers the same AEs repeatedly during the applicable study period, the event will be counted only once for that period. Repeated events per subject will be summarized according to the following rule: if a subject suffered the same AE more than once, the event will be assigned the worst severity, the closest relationship to the study drug and the earliest starting date. Only treatment emergent AEs will be reported. In the listings, however, all occurrences of the AEs will be presented.

For each unique treatment, treatment emergent AEs will be summarized per primary SOC, per HLT by primary SOC and per PT by HLT and primary SOC. Severity and drug-event relationship of treatment emergent AEs are summarized separately. Non-TEAEs will be listed.

Vitals signs, including changes from baseline will be summarized. A frequency table will be presented for markedly abnormal values.

10.5 Other Assessments

The assignment of subjects to subject samples, the disposition of subjects with respect to premature termination, reason for premature termination, drug exposure and treatment compliance will be summarized per treatment group.

Demographics and other baseline characteristics will be summarized per treatment group.

Medical history, including coding data will be summarized per primary SOC, per HLT by primary SOC and per PT by HLT and primary SOC.

Major protocol deviations will be listed.

Concomitant medication, including coding data will be summarized per assigned treatment period for incidence per subject, for primary therapeutic subgroup (3rd level ATC code) and for generic name by therapeutic subgroup.

10.6 Subgroup Analysis

Key efficacy and safety results will be summarized across subgroups defined by age group (3 – < 24 months, 2 years to 11 years, 12 to < 18 years).

10.7 Interim Analysis

not applicable

10.8 Determination of Sample Size

The sample size of this study is based on the results obtained with a randomized, double blind, study with Racecadotril in the treatment of hospitalized children aged 3-60 months suffering from acute watery diarrhea (Bio-Projet Study nr. 45, Salazar Lindo et al. 1998). A total of 135 subjects were analyzed in this study. Data of the study showed following recovery rates over time:

Duration of treatment	Percentage of recovered patients		Sample size per group required for a power of 80% using log-rank test (+10% drop out rate)
	Placebo	Racecadotril	
after 1 day (24 hours)	18.3%	46.6%	41 (46)
After 2 days (50 hours)	35.8%	70.1%	36 (40)
After 3 days (72 hours)	59.4%	84.2%	55 (62)
After 4 days (96 hours)	76.3%	90.1%	119 (132)
After 5 days (120 hours)	80.6%	94.7%	90 (100)

The mean duration of diarrhea was 64 (± 4.6) hours in the placebo group (median 64 hours) and 40 (± 4.1) hours in the Racecadotril group (median 28 hours), Therefore an appropriate approach to investigate a difference between recovery rates of the two treatment groups would be after a treatment duration of at least 3 days (i.e 72 hours). When the sample size in each group is 55 (with a total number of recoveries of at least 26), the two-sided log-rank test for equality of survival curves will have 80% power to detect the difference between 84.2% rate of recovery in the Racecadotril group and the 59.4% rate of recovery in the placebo group after a treatment duration of 72 hours. Adding a 10% drop-out rate the sample size per groups would be 62 subjects i.e. 124 subjects in total.

A minimum number of 20 subjects should be available in each age group (3 – < 24 months, 2 years to 11 years, 12 to < 18 years). A subgroup analysis per age group (3 – < 24 months, 2 years to 11 years, 12 to < 18 years) will be performed.

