The mean duration of diarrhea was 64 (± 4.6) hours in the placebo group (median 64 hours) and 40 (± 4.1) hours in the Racecadotril group (median 28 hours). Therefore an appropriate approach to investigate a difference between recovery rates of the two treatment groups would be after a treatment duration of at least 3 days (i.e. 72 hours). When the sample size in each group is 55 (with a total number of recoveries of at least 26), the two-sided log-rank test for equality of survival curves will have 80% power to detect the difference between 84.2% rate of recovery in the Racecadotril group and the 59.4% rate of recovery in the placebo group after a treatment duration of 72 hours. Adding a 10% drop-out rate the sample size per groups would be 62 subjects i.e. 124 subjects in total. A minimum number of 20 subjects should be available in each age group (3 – < 24 months, 2 years to 11 years, 12 to < 18 years). A subgroup analysis per age group (3 – < 24 months, 2 years to 11 years, 12 to < 18 years) will be performed.

TABLE OF CONTENTS

CLINICAL STUDY PROTOCOL	1
SYNOPSIS.....	2
LIST OF ABBREVIATIONS AND DEFINITION OF TERMS.....	13
1 ETHICS.....	15
1.1 Independent Ethics Committee or Institutional Review Board	15
1.2 Ethical Conduct of the Study	15
1.3 Subject Information and Consent.....	15
2 INTRODUCTION.....	17
3 STUDY OBJECTIVES.....	19
3.1 Primary Objective(s)	19
3.2 Secondary Objective(s)	19
3.3 Safety Objective(s).....	19
4 STUDY DESIGN.....	20
4.1 Overall Study Design and Plan-Description	20
4.2 Discussion of Study Design, Including the Choice of Control Groups	21
5 SELECTION OF STUDY POPULATION.....	22
5.1 Inclusion Criteria.....	22
5.2 Exclusion Criteria	22
6 REMOVAL OF SUBJECTS FROM THERAPY OR ASSESSMENT.....	24
7 TREATMENTS.....	25
7.1 Treatments to Be Administered	25
7.2 Packaging and Labeling	25
7.3 Storage and Dispensing of Study Drug.....	26
7.4 Method of Assigning Subjects to Treatment Groups.....	26
7.5 Selection of Doses and Timing in the Study.....	26
7.6 Blinding and Treatment Code Information	26
7.7 Prior and Concomitant Therapy.....	27
7.8 Treatment Compliance.....	28

8	STUDY ASSESSMENTS AND FLOW CHART	29
8.1	Efficacy Measurements	29
8.2	Safety Measurements	29
8.3	Other Assessments	30
8.4	Appropriateness of Measurements	31
8.5	Primary Efficacy/ Variable(s)	31
8.6	Flow Chart of Study Assessments	31
9	ADVERSE EVENTS.....	33
9.1	Adverse Events	33
9.1.1	Recording of Adverse Events	33
9.1.2	Follow-up of Adverse Events	35

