4.2.1 Primary Efficacy Analysis

The primary efficacy variable is the duration (hours) of diarrhea (treatment duration max 5 days). Duration of diarrhea is defined by date ("event" date) of the evacuation of the last diarrheal/watery stool before recovery.

In order to compare the primary efficacy parameter, duration of diarrhea, between the treatment groups, a Kaplan Meier (KM) analysis will be performed. The KM algorithm will be applied to derive the median duration and the 95% confidence intervals for the median, Q1, Q3 and mean duration with Greenwood's estimator of standard deviation of Kaplan-Meier estimator.

The log-rank test will be used to test whether the difference between the duration of diarrhea between two treatment groups is statistically significant, i.e. p-value <0.05.

For duration estimation the date and time of first drug intake will be assumed as start time point and all subjects without "event" will be censored by 6 days (144 hours).

SAS code for the analysis:

PROC LIFETEST DATA = [dataset name] METHOD=KM PLOTS=SURVIVAL OUTSURV=SURV CONFTYPE=LOGLOG ATRISK; TIME [time variable]*[censor variable]; STRATA [arm variable];

RUN;

The "OUTSURV=SURV" statement provides variables that contains the lower and upper limits of the pointwise confidence intervals for the survivor function ("SDF_LCL" and "SDF_UCL"), this confidence intervals should be transformed for tables as follows:

[Lower limit var name] = round(100*(1-SDF_UCL),.1); [Upper limit var name] = round(100*(1-SDF_LCL),.1);

As a first sensitivity analysis, duration of diarrhea will be analyzed by age subgroups as follows:

- Racecadotril + ORS (age subgroup 3 to < 24 month) vs ORS (age subgroup 3 to < 24 month) comparison;
- Racecadotril + ORS (age subgroup >= 2 to <12 years) vs ORS (age subgroup >= 2 to <12 years) comparison;
- Racecadotril + ORS (age subgroup 12 to < 18 years) vs ORS (age subgroup 12 to < 18 years) comparison;

As a second sensitivity analysis, duration of diarrhea will be analyzed by weight/dosing subgroups as follows:

• Racecadotril + ORS (Infants less than 9 kg) vs ORS (Infants less than 9 kg) comparison;

- Racecadotril + ORS (Infants from 9 kg to < 13 kg) vs ORS (Infants from 9 kg to < 13 kg Infants from 9 kg to < 13 kg) comparison;
- Racecadotril + ORS (Children from 13 kg to 27 kg) vs ORS (Children from 13 kg to 27 kg) comparison;
- Racecadotril + ORS (Children from more than 27 kg to 60 kg) vs ORS (Children from more than 27 kg to 60 kg) comparison;

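### The sample-size calculation enters the percentage recovered as the event-free proportion, so the 26 required recoveries, the stated 80% power and four of the five tabulated sample sizes are wrong (conservatively for the chosen n)

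*Protocol*

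**What the plan says.** Protocol section 10.8 tabulates the percentage of patients recovered at 24, 50, 72, 96 and 120 hours in an earlier placebo-controlled study. Beside each pair of rates is a column headed "Sample size per group required for a power of 80% using log-rank test (+10% drop out rate"), with 41, 36, 55, 119 and 90 per group. The 72-hour row is chosen: "When the sample size in each group is 55 (with a total number of recoveries of at least 26), the two-sided log-rank test" is said to have 80% power for the difference between the "84.2% rate of recovery in the Racecadotril group and the 59.4% rate of recovery in the placebo group after a treatment duration of 72 hours". A 10% drop-out allowance raises 55 to 62 per group, 124 in total. The synopsis repeats the table and the sentence.

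Protocol section 10.3 sets significance at a p-value below 0.05. SAP section 4.2.1 defines the event by the date "of the evacuation of the last diarrheal/watery stool before recovery" and censors subjects without it. The SAP turns Kaplan-Meier survival into a percentage with the event by taking 1 minus survival, as in "round(100*(1-SDF_UCL),.1").

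**The concern.** In the planned analysis a child who has recovered has had the event, and a child still ill is event-free. The tabulated percentages are therefore event proportions. Two features of section 10.8 suggest that they were used the other way round:

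- A requirement of 26 recoveries does not fit the table above it. The 24-hour row alone implies 55 × (0.183 + 0.466) = 35.7 recoveries in the first day.
- The required sample size rises steeply at 96 and 120 hours, when most children have recovered and events are most plentiful. That is what happens if non-recovery is treated as the event.

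At stake are the stated power, the stated event count and the comparison of time points that together justify randomising 124 children.

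**Working it through.** **Inputs.** Two-sided alpha 0.05 (Protocol 10.3 and 10.8), power 80%, 1:1 allocation, and the recovery rates in the Protocol 10.8 table. (1.960 + 0.8416)² = 7.849.

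**Formulas**, with S the event-free proportion and HR = ln S(racecadotril) / ln S(placebo):

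- Freedman events: d = 7.849 × ((1 + HR)/(1 − HR))²
- Schoenfeld events: d = 4 × 7.849 / (ln HR)²
- n per group = d / (2 − S(placebo) − S(racecadotril))

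**Reproducing the plan's figures.** Take S as the percentage recovered. At 72 hours:

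- HR = ln 0.842 / ln 0.594 = 0.330
- Freedman d = 7.849 × (1.330/0.670)² = 30.95, and n = 30.95 / (0.406 + 0.158) = 54.9, rounded up to 55
- Schoenfeld d = 31.40 / 1.108² = 25.6, rounded up to 26

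The Freedman count of 31 equals the number of children expected not to have recovered at 72 hours: 55 × (0.406 + 0.158) = 31.0. The stated n is thus the Freedman figure, while the stated 26 is the Schoenfeld figure for the same reversed input.

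**All five rows, in both orientations (n per group, rounded up):**

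| Time | Stated | Freedman, S = recovered | Freedman, S = 1 − recovered | Schoenfeld, S = 1 − recovered |
|---|---|---|---|---|
| 24 h | 41 | 40.30 → 41 | 46.01 → 47 | 37.71 → 38 |
| 50 h | 36 | 35.30 → 36 | 34.58 → 35 | 29.52 → 30 |
| 72 h | 55 | 54.88 → 55 | 46.29 → 47 | 42.60 → 43 |
| 96 h | 119 | 118.70 → 119 | 87.15 → 88 | 83.99 → 84 |
| 120 h | 90 | 89.21 → 90 | 55.72 → 56 | 52.71 → 53 |

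The reversed Freedman column matches every stated value. Schoenfeld with the reversed input (37, 30, 46, 103, 68) does not. Nor do comparisons of two proportions, without continuity correction (42, 33, 51, 115, 85) or with it (49, 38, 59, 129, 98).

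**72 hours with recovery as the event:**

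- HR = ln 0.158 / ln 0.406 = 2.047
- Recoveries required: Freedman 7.849 × (3.047/1.047)² = 66.5, so 67; Schoenfeld 31.40 / 0.716² = 61.2, so 62
- Recoveries expected from 55 per group: 55 × (0.594 + 0.842) = 79.0
- Power, Freedman: Φ(√79.0 × 1.047/3.047 − 1.96) = Φ(1.09) = 86.3%
- Power, Schoenfeld: Φ(√79.0 × 0.716/2 − 1.96) = Φ(1.22) = 88.9%

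**Proportional hazards.** Both formulas assume them, but the table does not show them. The hazard ratios for recovery in successive intervals are 3.10, 2.41, 1.39, 0.87 and 3.12. A log-rank test simulated on the full tabulated curves (20,000 runs, 55 per group, no drop-out, constant hazard between tabulated times) has about 96% power to 72 hours and 95% to 120 hours. Linear incidence between the times changes these by less than one percentage point. Using only the 120-hour row (HR 1.791, 96.4 expected recoveries) gives 79.5% (Freedman) to 81.6% (Schoenfeld).

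**The case against.** The strongest objection is that nothing in the trial turns on this. Size is fixed at 124, Protocol section 10.7 provides for no interim analysis, and reaching 26 recoveries triggers nothing. The error is on the safe side at the row that was used, the other four rows did not set n, and the SAP analysis has the event the right way round. All of that stands. It bears on how serious the error is, not on whether it is one.

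Three narrower objections have some force:

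- The protocol names no formula. That n is Freedman's and 26 is Schoenfeld's is inferred from matching numbers. For n the inference is strong, with five exact matches; for the 26 it rests on one rounded value. The contradiction between 26 recoveries and the table does not depend on it.
- The direction of error at 24 hours depends on the formula. The stated 41 is too low by Freedman (47 needed, power about 75%) but sufficient by Schoenfeld (38 needed, power about 83%). The count of four wrong rows uses Freedman and treats the one-subject difference at 50 hours as immaterial; by Schoenfeld all five rows differ.
- The 86 to 89% range spans two formulas and assumes proportional hazards, which the table contradicts; the simulation to 72 hours gives 96%. The range is the like-for-like replacement for the protocol's single-time-point 80%, and should be labelled as such.

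**Conclusion.** The point holds. The percentage recovered was used as the event-free proportion, and the figures derived from it are wrong on the protocol's own rates:

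- The recoveries needed at 72 hours are 62 to 67, about 2.5 times the stated 26.
- The power of 55 evaluable children per group is 86 to 89% by formula, not 80%.
- By Freedman the 72-, 96- and 120-hour rows are too high by 8, 31 and 34 per group, the 24-hour row is too low by 6, and the 50-hour row is essentially unchanged.

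These figures assume that the earlier study's rates apply here; the formula power also assumes proportional hazards. The error does not leave the trial underpowered: the same formula with the right orientation gives 47 per group, or 53 after the 10% allowance (47/0.9 = 52.2), against 62 planned. What fails is the written justification, which should be corrected.

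**What to change.** In Protocol section 10.8 and the synopsis:

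1. Recompute the table with survival equal to 1 minus the recovery percentage, and name one formula for both sample size and events. With Freedman the rows become 47, 35, 47, 88 and 56, with 67 recoveries required and 86% power for 55 per group at 72 hours. With Schoenfeld they become 38, 30, 43, 84 and 53, with 62 recoveries and 89% power.
2. Replace the 26 with the figure from the chosen formula, and state that recovery is the event.
3. Label the 72-hour power as assuming proportional hazards. For the five-day log-rank test in the SAP, compute power from the full tabulated curves (about 95% under the assumptions above). If the 80 to 82% from the 120-hour row is quoted at all, mark it as a conservative, proportional-hazards figure.
4. Keep 124 randomised.

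The cost is wording and table figures. Enrolment, the test, alpha and the SAP analysis do not change.

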11 INVESTIGATOR OBLIGATIONS

The Investigator agrees to conduct the clinical study in compliance with this protocol which was approved by the IEC/IRB in compliance with local regulatory requirements. The Investigator and the Sponsor will sign the protocol to confirm this agreement.

11.1 Essential Study Documents

The Investigator is responsible for providing and maintaining essential study documents. Essential study documents are those documents that individually and collectively permit the evaluation of the conduct of the study and the quality of the data produced. These documents serve to demonstrate the compliance of the Investigator and the Sponsor (or an authorized representative) with the standards of GCPs and with all applicable national regulatory requirements.

Essential study documents will include regulatory documents as well as source documents which are original documents, data and records of clinical findings, observations and other activities in a clinical study necessary for the reconstruction and evaluation of the study. Source documents will include hospital records, clinical and office charts, laboratory notes, memoranda, subject diaries or evaluation checklists, pharmacy dispensing records, recorded data from automated instruments, copies or transcriptions certified after verification as being accurate copies, microfiches, photographic negatives, microfilm or magnetic media, x-rays, subject files and records kept at the pharmacy, at the laboratories and at medical/technical departments involved in the clinical study.

The Investigator agrees to allow direct access to all essential clinical study documents for the purpose of monitoring and/or auditing by the Sponsor (or an authorized representative) and inspection by the appropriate national and foreign regulatory authorities.

11.2 Case Report Form (CRF) Completion

Data reflecting the subject's participation with the study drug under investigation will be reported to the Sponsor (or an authorized representative). The data will be recorded on the designated (e)CRFs provided or approved by the Sponsor.

The (e)CRF is essentially considered a data entry form and should not constitute the original (or source) medical records unless otherwise specified. Source documents are all documents used by the Investigator or hospital that relate to the subject's medical history, that verify the existence of the subject, the inclusion and exclusion criteria and all records covering the subject's participation in the study. They include laboratory notes, ECG results, memoranda, pharmacy dispensing records, patient files, etc.

The Investigator is responsible for maintaining source documents. These will be made available for inspection by the study monitor at each monitoring visit. The Investigator must submit a completed (e)CRF for each subject who did not fail screening. All supportive documentation

submitted with the (e)CRF, such as laboratory or hospital records, should be clearly identified with the study and subject number. Any personal information, including subject name, should be removed or rendered illegible to preserve individual confidentiality.

All data must be entered in English. The (e)CRFs should always reflect the latest observations on the subjects participating in the trial. Therefore, the (e)CRFs are to be completed as soon as possible after the subject's eligibility has been confirmed and thereafter during or after the subject's visit. To avoid inter observer variability, every effort should be made to ensure that the same individual who made the initial baseline determinations completes all efficacy and safety evaluations. The Investigator must verify that all data entries in the (e)CRFs are accurate and correct. If some assessments are not done, or if certain information is not available or not applicable or unknown, the Investigator should indicate this in the (e)CRF. The Investigator will be required to (electronically) sign off on the clinical data.

The monitor will review the (e)CRFs and evaluate them for completeness and consistency. The (e)CRF will be compared with the source documents to ensure that there are no discrepancies between critical data. All entries, corrections and alterations are to be made by the responsible Investigator or his/her designee. The monitor is not allowed to enter data in the (e)CRFs.

If additional corrections are needed, the responsible monitor or Data Manager will raise a query. The appropriate investigational staff will answer queries sent to the Investigator.

In case screen failure data is entered in the (e)CRF, these data should be clearly indicated in the raw datasets and removed from the analysis datasets.

